19.5.2 Power Analysis

- Because the goal of this RCT is to assess study feasibility of a future trial, rather than efficacy comparisons, we did not conduct a formal power calculation. Rather, we established a sample size of 22 patients based on clinical expertise, annual PPMC isolated CABG surgical volume, and knowledge of operating room procedures. Given this low number of projected trial enrollment (n=22), this feasibility RCT will be underpowered to detect a difference in cardiac surgical outcomes. Nevertheless, we plan to review the electronic medical record for each study arm of the trial to compare any potential differences in clinical outcomes between the default and the as-needed intraoperative TEE trial arms.

Clinical Study Number:	NCT06154265	Document Title:	10/24/2024	Page 36 of 36
		Default vs As-Needed Intraoperative Transesophageal Echocardiography (TEE) in Low-Risk Isolated Coronary Artery Bypass Graft (CABG) Surgery: A Randomized Controlled Trial

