8.7 Study Termination

- This study may be suspended or terminated at any time by the will of the NIH, NHLBI, UPenn IRB, or the FDA.

Clinical Study Number:	NCT06154265	Document Title:	10/24/2024	Page 17 of 36
		Default vs As-Needed Intraoperative Transesophageal Echocardiography (TEE) in Low-Risk Isolated Coronary Artery Bypass Graft (CABG) Surgery: A Randomized Controlled Trial		

9 Sites

This is a single site study being conducted at Penn Presbyterian Medical Center (PPMC), a site within the University of Pennsylvania Health System.

10 Data Management and Statistical Analysis Plan

The study data will be captured on Case Report Forms (CRF), as appropriate. The study data, including adverse events, will be summarized for final reports to NHLBI and the NIH. Only staff delegated by the PI ([name]) will have access to the data.

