10.3 Sample Size and Power Determination

- To account for screen failures (i.e., exclusions after enrollment), we are planning to obtain informed consent for up to 75 patients to ensure we achieve our enrollment goal of 22 patients randomized to each trial arm.

Clinical Study Number:	NCT06154265	Document Title:	10/24/2024	Page 18 of 36
		Default vs As-Needed Intraoperative Transesophageal Echocardiography (TEE) in Low-Risk Isolated Coronary Artery Bypass Graft (CABG) Surgery: A Randomized Controlled Trial		

11 Risk and Benefit Analysis

The standard-of-care intraoperative TEE device has passed quality assurance testing according to international regulatory guidelines. But specific to low-risk, isolated CABG surgery, the risk vs benefit profile for intraoperative TEE as an invasive hemodynamic monitoring device is currently unknown. Consequently, given that neither arm of the trial will be deprived of intraoperative TEE, the benefits of a greater understanding of who, when, and why intraoperative TEE should be used in isolated CABG surgery outweigh the risks in participating in a trial randomizing patients to two standard-of-care trial arms. The concrete risks associated with RCT participation and the steps put in place to mitigate these risks will be reviewed.

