19.2.1.1 Estimated Rates of RCT Enrollment

- We will recruit up to 75 isolated CABG surgery patients who present to the cardiac surgery clinic(s) at either PPMC or the Hospital of the University of Pennsylvania. The Division of Cardiovascular Surgery, within the University of Pennsylvania Health System is the largest cardiac surgery division in the State of Pennsylvania and receives over 250 isolated CABG referrals per year. This breaks down to approximately 20 patients per month. Assuming half of these patients meet inclusion criteria (i.e. 10 potential subjects per month), to meet our sample size of 22 isolated CABG surgery patients in year, we would need a 20% participation rate over 12 months; equating to approximately 2 – 3 study subjects per month. Although we do not anticipate difficulty in recruitment, if we are unable to achieve our

Clinical Study Number:	NCT06154265	Document Title:	10/24/2024	Page 33 of 36
		Default vs As-Needed Intraoperative Transesophageal Echocardiography (TEE) in Low-Risk Isolated Coronary Artery Bypass Graft (CABG) Surgery: A Randomized Controlled Trial		

projected sample size goal within one year, we will extend the recruitment period six months.

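### Section 10.3 plans 22 randomized patients per arm (44), the appendix plans 22 in total, and the 20% participation rate fits only the smaller figure

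*Combined protocol and SAP*

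**What the plan says.** Section 10.3 (Sample Size and Power Determination) gives "our enrollment goal of 22 patients randomized to each trial arm", and to allow for exclusions after consent it adds that "we are planning to obtain informed consent for up to 75 patients". With two parallel arms this is 44 randomized patients.

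Section 19.5.2 (Power Analysis) reports that no formal power calculation was done and that "we established a sample size of 22 patients based on clinical expertise", among other practical considerations. It then applies the same number to the whole trial: "Given this low number of projected trial enrollment (n=22), this feasibility RCT will be underpowered".

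Section 19.2.1.1 (Estimated Rates of RCT Enrollment) repeats the ceiling of 75 but projects accrual for 22: "to meet our sample size of 22 isolated CABG surgery patients in year, we would need a 20% participation rate over 12 months". It puts this at roughly 2 to 3 subjects a month. The pool behind the projection is the health-system cardiac surgery division, which "receives over 250 isolated CABG referrals per year". The plan rounds this to 20 a month and takes half as eligible. If the goal is missed in one year, recruitment is extended by six months.

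**The concern.** The trial has two sizes, one twice the other, and both stand in current text. The accrual projection was built for the smaller one, so a reader who takes Section 10.3 as the plan has no recruitment rate that matches it.

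The practical stakes are these:

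- The size decides when enrollment closes. If 24 patients were randomized, the appendix goal would be met, while under Section 10.3 the trial would stand at 24/44 = 55% of its goal.
- Section 19.1.1.4 asks the DSMB to assess recruitment and accrual, and the documents give it two goals to assess them against.
- The second co-primary is the rate of TEE among patients randomized to the as-needed arm. Its precision depends on whether that arm holds 22 patients or about 11.

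**Working it through.** **Inputs.** From Section 19.2.1.1: about 20 referrals a month, half eligible (10 a month), 20% participation, 12 months of recruitment with a possible 6 more. From Section 10.3: 22 per arm × 2 arms = 44 randomized.

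**Step 1: reproduce the plan's figure.** Expected accrual = eligible per month × participation × months = 10 × 0.20 × 12 = 24. The exact rate needed for 22 is 22/(10 × 12) = 18.3%, which is close to the stated 20%. The figure of 22 therefore reproduces as a trial total. It does not reproduce as a per-arm number, because 44 would need 44/120 = 36.7%.

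**Step 2: the same inputs applied to 44.**

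| Window | Eligible | Expected at 20% | Rate needed for 44 | Patients per month for 44 |
|---|---|---|---|---|
| 12 months | 10 × 12 = 120 | 24 | 44/120 = 36.7% | 44/12 = 3.67 |
| 18 months | 10 × 18 = 180 | 36 | 44/180 = 24.4% | 44/18 = 2.44 |

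Using 250 referrals a year without rounding, the eligible pool is 125 or 187.5, expected accrual is 25 or 37.5, and the rate needed is 35.2% or 23.5%. The conclusion is the same.

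**Step 3: chance variation.** If each eligible patient joins with probability 20%, the binomial probability of 44 or more in 18 months is about 8% with 180 eligible and about 14% with 188. At 2 a month, 44 patients take 44/2 = 22 months. That is beyond the 18-month recruitment window but inside the 24-month study duration in the synopsis.

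**Step 4: precision in the as-needed arm.** With equal allocation the arm holds 22 patients under Section 10.3 or 22/2 = 11 under the appendix. The documents give no expected TEE rate, so the rates below are assumptions, chosen so that both arm sizes have the same observed proportion. Intervals are exact (Clopper-Pearson) 95%.

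| Assumed rate | Arm of 22 | Arm of 11 |
|---|---|---|
| 0% | 0/22: 0% to 15% | 0/11: 0% to 28% |
| 18% | 4/22: 5% to 40% | 2/11: 2% to 52% |
| 36% | 8/22: 17% to 59% | 4/11: 11% to 69% |

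**The case against.** The strongest reply is that this is an unpowered feasibility trial with no confirmatory test, and that the intended size can be guessed. The ceiling of 75 consents appears in both places, and it sits better with 44 randomized (44/75 = 59%) than with 22 (22/75 = 29%). That makes Section 10.3 the likelier current figure and softens the error. It does not remove it, because no passage says so and Section 19.5.2 attaches 22 to the trial as a whole.

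A reader might also infer several stronger things that the documents do not support:

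- **That the plan cannot reach 44.** The 20% is a rate worked back from 22, not a forecast. The plan also quotes 2 to 3 subjects a month, and 44 in 18 months needs 2.44. The referral volume is given as a minimum. What can be said is that at 20% of the stated pool the expected number falls short.
- **That only about 21 would be randomized.** This comes from multiplying 36 by 44/75. However, Section 19.2.1.1 matches the 20% to the final sample size, and 75 is a ceiling rather than an expected yield, so the calculation probably discounts twice.
- **That the recruitment co-primary is measured against a doubled target.** Section 6.1 defines it as enrolled divided by screened. Neither 22 nor 44 enters it, and no success threshold is tied to the sample size.
- **That 2 to 3 a month is an arithmetic error.** Against 22/12 = 1.8 or 10 × 0.20 = 2.0, with the plan's own word of approximation, this is loose rounding.
- **That single-site recruitment makes the requirement higher by a known amount.** Section 9 does name one hospital while the 250 referrals are division-wide, but no volume for that hospital is given. The direction is plausible and the size is unknown.

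**Conclusion.** The concern holds as an internal contradiction with an arithmetic consequence. Section 10.3 plans 44 randomized patients. Sections 19.5.2 and 19.2.1.1 plan 22, and the accrual sum confirms that this 22 is a total.

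For 44, the stated 20% gives an expected shortfall of 44 − 24 = 20 patients at 12 months and 44 − 36 = 8 at 18 months. This rests on the plan's own pool of 10 eligible patients a month and on counting the 20% as final subjects, as Section 19.2.1.1 does. The halving of the as-needed arm assumes equal allocation, and the intervals are illustrations at assumed rates.

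No hypothesis test is compromised. It should still be corrected before the plan is relied on, because the trial's size is ambiguous by a factor of two and the stated recruitment rate is valid for only one of the two sizes.

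**What to change.** State one sample size in Sections 10.3, 19.2.1.1 and 19.5.2. If Section 10.3 is current:

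- Change both appendix sections to 44 randomized (22 per arm) from up to 75 consents.
- Replace the 20% and the 2 to 3 a month with the rates needed for 44: about 37% of eligible patients, or 3.7 a month, over 12 months; about 24%, or 2.4 a month, over 18 months.
- Say whether these rates count consented or randomized patients, since Section 10.3 expects losses between the two.
- Base the eligible pool on the hospital or hospitals that will actually recruit. Section 9 names a single site, while inclusion criterion 1 and Section 19.2.1.1 are wider, so these need to agree. The rates above should then be recalculated from that volume.

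If 22 in total is current, Section 10.3 has to change instead, and the ceiling of 75 consents should be justified for that size.

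The cost is rewording in these sections and obtaining a volume figure for the recruiting hospitals. If 44 is kept, the stated recruitment requirement becomes less favourable. No patients are added beyond Section 10.3.
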